7.3.2 Persistent or Recurrent Adverse Events

A persistent adverse event is one that extends continuously, without resolution, between patient evaluation timepoints. Such events should only be recorded once on the Adverse Event eCRF. The initial severity (intensity or grade) of the event will be recorded at the time the event is first reported. If a persistent adverse event becomes more severe, the most extreme severity should also be recorded on the Adverse Event eCRF. If the event becomes serious, it should be reported to the Sponsor immediately (i.e., no more than 24 hours after learning that the event became serious; see [Section 7.3.4](#) for reporting instructions). The Adverse Event eCRF should be updated by changing the event from "non-serious" to "serious," providing the date that the event became serious, and completing all data fields related to serious adverse events.

A recurrent adverse event is one that resolves between patient evaluation timepoints and subsequently recurs. Each recurrence of an adverse event should be recorded as a separate event on the Adverse Event eCRF.

7.3.3 Adverse Events in Individuals not Enrolled in the Study

If an adverse event inadvertently occurs in an individual not enrolled in the study (e.g., during administration of study drug), the Adverse Event Form provided to investigators should be completed and submitted to Roche or its designee, either by faxing or by scanning and emailing the form using the fax number or email address provided to investigators.

7.3.4 Immediate Reporting Requirements from Investigator to Sponsor

Certain events require immediate reporting to allow the Sponsor to take appropriate measures to address potential new risks in a clinical trial. The investigator must report such events to the Sponsor immediately; under no circumstances should reporting take place more than 24 hours after the investigator learns of the event. The following is a list of events that the investigator must report to the Sponsor within 24 hours after learning of the event, regardless of relationship to study drug:

- Serious adverse events (see [Section 7.3.4.1](#) for further details)
- Non-serious adverse events of special interest (see [Section 7.3.4.2](#) for further details)
- Pregnancies (see [Section 7.3.4.2.3](#) for further details)

The investigator must report new significant follow-up information for these events to the Sponsor immediately (i.e., no more than 24 hours after becoming aware of the information). New significant information includes the following:

- New signs or symptoms or a change in the diagnosis
- Significant new diagnostic test results
- Change in causality based on new information
- Change in the event's outcome, including recovery
- Additional narrative information on the clinical course of the event

Investigators must also comply with local requirements for reporting SAEs to the local health authority and IRB/EC.

7.3.4.1 Reporting of Serious Adverse Events

Only SAEs caused by a protocol mandated intervention that are experienced after the patient has signed the Informed Consent form but before they have received study treatment should be reported as SAEs. Any clinical adverse event or abnormal laboratory test value that is *serious* and which occurs during the course of the study (as defined in [Section 7.2.1.3](#) above), must be reported to Roche **within 24 hours** of the Investigator becoming aware of the event (expedited reporting).

The Investigator is not required to actively monitor patients for adverse events after the end of the adverse event reporting period (defined as 28 days after the last dose of study drug). However the Sponsor should be notified if the Investigator becomes aware of any SAE that occurs after the end of the adverse event reporting period, if the event is believed to be related to prior study drug treatment. After the study site has closed, the Investigator should report adverse reactions as mandated in the protocol directly to the Local Drug Safety Affiliate using a paper SAE form. Paper SAE forms and contact details for the Local Drug Safety Affiliate will be provided to the investigational site at close-out.

Suspected Unexpected Serious Adverse Reactions (SUSARs) are reported to Investigators at each site and associated IRB/IEC when the following conditions occur:

- The event must be a SAE.
- There must be a certain degree of probability that the event is an adverse reaction from the administered drug.
- The adverse reaction must be unexpected, that is to say, not foreseen in the Investigator's Brochure.

When all subjects at a particular site are off treatment as defined by the protocol:

- only individual SUSAR reports originating in that particular trial will be forwarded to the site and associated IRB/IEC on an expedited basis;
- individual SUSARs considered to be a significant safety issue and/or which result in Roche recommending a change to the Informed Consent Form (ICF), will be reported in an expedited manner to all Investigators and IRBs/IECs;

SUSAR reports originating from other trials using the same IMP will be provided as six monthly SUSAR Reports (SSRs) to Investigators and IRBs/IECs where long-term follow-up studies are carried out, unless they are considered significant.

All adverse events must be collected and reported during the study and for up to 28 days after the last dose of study medication.

This study adheres to the definition and reporting requirements of **ICH Guideline for Clinical Safety Data Management, Definitions and Standards for Expedited Reporting, Topic E2**. Complete information can be found in [Appendix 8](#).

7.3.4.2 Reporting of Protocol-Defined Events of Special Interest

7.3.4.2.1 Abortion, Congenital Anomaly, and Birth Defects

Abortions, congenital anomalies, and birth defects are events of special interest and will need to be reported to the Sponsor expeditiously.

Abortion, whether accidental, therapeutic, or spontaneous, should always be classified as serious (as the Sponsor considers these medically significant), recorded on an SAE eCRF page, and expeditiously reported to the Sponsor.

Any congenital anomaly/birth defect in a child born to a female patient or female partner of a male patient exposed to the investigational product should be recorded and reported as an SAE.

7.3.4.2.2 Cutaneous Squamous Cell Carcinoma / Keratoacanthoma & Second Primary Malignancies

Cutaneous squamous cell carcinoma (cSCC), Keratoacanthoma (KA), basal cell carcinoma (BCC) and any other second primary malignancies and its progression or recurrence are defined as events requiring close monitoring. With the exception of events of actinic keratosis, these events must always be designated as SAEs in order to ensure their reporting to the Health Authorities in an appropriate and timely manner. The treating physician is asked to perform regular (at each study visit) skin exams of the patient. A full skin examination by a dermatologist is requested during the Screening Period, after 28 days of vemurafenib treatment, every 12 weeks thereafter during the Treatment Period, at the End of Treatment Visit, and at the Safety Follow-Up Visit. Any lesion at baseline or during treatment clinically suspected of representing cutaneous, basal cell carcinoma, actinic keratosis, keratoacanthoma or other skin conditions identified by the dermatologist should be treated as per local standard of care.

If more than one SCC lesion occurs in more than one location on the skin, and the multiple lesions are detected during the same observation period (i.e., clinic visit), then these SCC lesions should be reported together as one event on the same **SAE** form and also reported as one event on the **SAE or AE** page of the eCRF. Locations of each lesion can be listed in the event term and narrative for **SAEs or AE** reporting.

If more than one SCC lesion occurs in more than one location on the skin and the lesions are detected during separate observation periods (i.e., separate clinic visits), then these SCC lesions should be reported as separate events on separate **SAE** forms and also as separate events on the **SAE or AE** page of the eCRF.

Cases in which patients rapidly develop multiple lesions within a limited time-frame (e.g., 5–10 lesions over a 2-week period) will be handled on a case by case basis in terms of reporting. Please contact the Medical Monitor when these cases occur, for additional discussion.

Skin biopsies should be performed by a dermatologist, as necessary, with histopathologic interpretation of suspected lesions. Biopsy-proven non-melanoma skin cancers should be excised. Available excised cutaneous SCC/KA as well as from any suspicious lesions specimen block/sections should be sent to a designated central dermatopathology laboratory for confirmation of diagnosis.

Details including histological findings should be reported within the eCRF (see also [Section 5.3.8.4](#)).

SCC events should be reported in any case as an SAE as follows:

(a) In the SAE form in the eCRF

- Cutaneous SCC events should be reported using the event term of “Squamous Cell Carcinoma of the skin” or “Cutaneous Squamous Cell Carcinoma”.
- The term “Squamous Cell Carcinoma” should only be used if there is a confirmed non-cutaneous squamous cell carcinoma.
- If the SCC is confirmed to be cutaneous the term “Cutaneous Squamous Cell Carcinoma” or “Squamous Cell Carcinoma of the skin” should be used. Do not report the event term of “treatment related secondary malignancy” or “Squamous Cell Carcinoma”.
- If a cSCC or SCC is suspected, an SAE with the event term “suspected cutaneous SCC” or “suspected non-cutaneous of <insert organ site>” and onset date of admission has to be submitted within 24 hours.
- If the SCC has been confirmed by the local pathology laboratory, the SAE has to be updated with the event term “cutaneous SCC” or “non-cutaneous of <insert organ site>” explaining shortly in the comments section that the diagnosis has been confirmed. The onset date would still remain at the date of admission.
- For all SCC cases, the tick box medically significant must be ticked. The onset date for an SCC SAE is always the date of when the suspicion of an SCC occurred regardless of when and if the suspected diagnosis was confirmed.
- Events of actinic keratosis do not need to be reported as SAEs under the current cSCC reporting guidelines.

(b) In the eCRF AE form

- Cutaneous SCC events should be reported using the event term of “Squamous Cell Carcinoma of the skin” or “Cutaneous Squamous Cell Carcinoma” and should be designated as Grade 3 severity.
- The term “Squamous Cell Carcinoma” should only be used if there is a confirmed non-cutaneous squamous cell carcinoma.
- SCC events should be reported as “Squamous Cell Carcinoma”.
- If the SCC is confirmed to be cutaneous the term “Cutaneous Squamous Cell Carcinoma” or “Squamous Cell Carcinoma of the skin” should be used with a Grade 3 designation

Any second primary malignancies should be reported in any case as an SAE as follows:

(a) In the SAE form in the eCRF

Second primary malignancies should be reported with the type of malignancy. Do not report the event term of “treatment related secondary malignancy”.

(b) In the eCRF AE form

Second primary malignancies should be reported with the type of malignancy and a Grade 3 designation.

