7.2.1.1 Intensity

Intensity of all adverse events will be graded according to the NCI Common Terminology Criteria for Adverse Events, Version 4.0 (CTCAE, v4.0) on a five-point scale (Grade 1 to 5) and reported in detail on the eCRF.

Adverse events not listed on the CTCAE v4.0 should be graded as described in [Table 14](#).

Table 14:
Adverse Event Grading (Severity) Scale

CTC Grade	Equivalent to:	Definition
Grade 1	Mild	Discomfort noticed but no disruption of normal daily activity
Grade 2	Moderate	Discomfort sufficient to reduce or affect daily activity; no treatment or medical intervention is indicated although this could improve the overall well-being or symptoms of the patient
Grade 3	Severe	Inability to work or perform normal daily activity; treatment or medical intervention is indicated in order to improve the overall well-being or symptoms; delaying the onset of treatment is not putting the survival of the subject at direct risk.
Grade 4	Life threatening / disabling	An immediate threat to life or leading to a permanent mental or physical conditions that prevents work or performing normal daily activities; treatment or medical intervention is required in order to maintain survival.
Grade 5	Death	AE resulting in death

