The Investigator is not required to actively monitor patients for adverse events after the end of the adverse event reporting period (defined as 28 days after the last dose of study drug). The Investigator is not required to actively monitor patients for adverse events after the end of the adverse event reporting period (defined as 28 days after the last dose of study drug). However the Sponsor should be notified if the Investigator becomes aware of any SAE that occurs after the end of the adverse event reporting period, if the event is believed to be related to prior study drug treatment.

A pre-existing medical condition that is present at the start of the study should be recorded on the Medical History eCRF.

AEs will be reported and graded following NCI CTCAE, v4.0. Accordingly, intensity of all AEs will be graded on a five-point scale (Grade 1 to 5) and reported in detail on the CRF. Reporting of AE based on CTCAE terms and corresponding grading are an integral part of safety/AE/SAE reporting in this study and will have to be strictly followed. The causality relationship of study 'treatment' to the adverse event will be assessed by the Investigator as either **Yes** or **No**.

If there is a reasonable suspected causal relationship to the study treatment, i.e., there are facts (evidence) or arguments to suggest a causal relationship, drug-event relationship should be assessed as **Yes**.

The Investigator should provide his/her assessment as to whether an AE is related to the study treatment regimen.

The following criteria should be considered in order to assess the relationship as **Yes**:

- Reasonable temporal association with drug administration
- It may or may not have been produced by the patient's clinical state, environmental or toxic factors, or other modes of therapy administered to the patient
- Known response pattern to suspected drug

- Disappears or decreases on cessation or reduction in dose
- Reappears on rechallenge

The following criteria should be considered in order to assess the relationship as **No**:

- It does not follow a reasonable temporal sequence from administration of the drug
- It may readily have been produced by the patient's clinical state, environmental or toxic factors, or other modes of therapy administered to the patient
- It does not follow a known pattern of response to the suspected drug
- It does not reappear or worsen when the drug is re-administered

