8.3.3 Safety Data Analysis

The safety variables will be summarized for the safety population where the safety population is SP1 to SP7. All safety variables will be summarized for each cohort.

All AEs will be assessed according to the NCI CTCAE, v4.0, grading system. The analysis of AEs will focus on treatment-emergent AEs, i.e., AEs occurring on the day of or after first administration of study drug (vemurafenib). Non-treatment emergent AEs (i.e., those occurring before commencement of study medication) will only be listed.

The incidence, type, and severity of AEs will be summarized according to the primary system-organ class (SOC) and within each SOC, by MedDRA preferred term. Summary tables may be presented for time to first onset of the AE of special interest.

AEs leading to treatment interruption and discontinuation and SAEs will be analysed in a similar way to all AEs. Cause of death will also be summarized and listed.

Results from skin evaluation, head and neck evaluations, chest CT scan (e.g., number of lesions, SCC - keratoacanthoma type, etc.) will be summarized using frequencies and percentages. The number of patients prematurely discontinued from the treatment with corresponding reason for discontinuation will be summarized and listed. The discontinuation from study will be also summarized and listed.

Descriptive statistics will be presented for cumulative vemurafenib doses and duration of exposure.

Laboratory parameters, haematology, and serum biochemistry will be presented in shift tables of NCI-CTCAE grade at baseline versus worst grade during the Treatment Period. The summary of laboratory parameters presented by means, standard deviation, minimum, and maximum will be also presented.

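### Section 7.3.4.2.2 fixes every second primary malignancy at Grade 3 on the adverse event form, contradicting the protocol's CTCAE grading rule; one that is life-threatening or fatal when first reported is under-graded

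*Protocol*

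**What the plan says.** Two sets of instructions apply to the same field on the adverse event form.

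**The specific rule.** Protocol section 7.3.4.2.2 opens its paragraph on second cancers with "Any second primary malignancies should be reported in any case as an SAE as follows". It then treats the two forms separately. For the SAE form it asks for the type of malignancy and gives no grade. For the adverse event form it says "Second primary malignancies should be reported with the type of malignancy and a Grade 3 designation". The same section separately fixes Grade 3 for cutaneous squamous cell carcinoma (SCC). Its bullets on non-cutaneous SCC give no grade, but the general sentence on second primaries would cover such a case.

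**The general rule.** Section 7.2.1.1 says "Intensity of all adverse events will be graded according to the NCI Common Terminology Criteria for Adverse Events", version 4.0, "on a five-point scale (Grade 1 to 5) and reported in detail on the eCRF". Table 14 in that section, for events CTCAE does not list, puts immediate threats to life at Grade 4 and defines Grade 5 as "AE resulting in death". Section 7.3.1 says that CTCAE terms and "corresponding grading are an integral part of safety/AE/SAE reporting in this study and will have to be strictly followed". Section 7.2.1.3 requires severity and seriousness to be judged separately for each event.

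**The analysis.** Section 8.3.3 has all adverse events assessed by CTCAE v4.0 and their severity summarised by system organ class and preferred term. Section 8.1.3 lists adverse events of Grade 3 or 4 among the primary safety variables for each cohort.

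**The concern.** A fixed grade is harmless only if every event in the class truly has that grade. Second primary malignancy is a broad class. It can include internal cancers, and section 7.3.4.2.2 extends it to later course: "Keratoacanthoma (KA), basal cell carcinoma (BCC) and any other second primary malignancies and its progression or recurrence are defined as events requiring close monitoring". Section 7.1 also warns that the drug may cause cancers associated with RAS mutations to progress. Life-threatening or fatal events are therefore foreseeable, and for these a site cannot obey both rules.

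What is at stake is the severity summary for an event type that the protocol singles out for close monitoring. If sites follow the specific rule, the most severe cases are recorded below their CTCAE grade, and a death can be counted among the Grade 3 or 4 events. If some sites follow the general rule instead, the same event is graded differently from site to site.

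**Working it through.** The protocol gives no figure to reproduce. The check is to apply each rule to the same event and compare the entries. It assumes that Grade 4 means life-threatening and Grade 5 means death for events listed in CTCAE, as Table 14 states for unlisted ones. Appendix 7 gives only a link to CTCAE, so its text cannot be checked here.

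| Second primary malignancy | Grade under 7.2.1.1 and 7.3.1 | Entry under 7.3.4.2.2 | Severity table | Grade 3 or 4 count |
|---|---|---|---|---|
| Fatal when first reported | 5 | 3 | two grades too low (5 − 3) | wrongly included |
| Life-threatening when first reported | 4 | 3 | one grade too low (4 − 3) | unchanged, since 3 and 4 both count |
| Grade 3 throughout | 3 | 3 | correct | correct |
| First reported at Grade 3, worsens later | 3, then 4 or 5 | 3 at entry; section 7.3.2 has the worst severity recorded too | correct if 7.3.2 is applied | depends on how the later grade is used |

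The first two rows are the defect. Section 7.3.2 concerns a persistent event that becomes more severe, so it does not help an event that was already at its worst when first entered. It also does not say that it takes precedence over section 7.3.4.2.2.

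**Size of a single case.** Suppose one fatal second primary is entered as Grade 3, and the patient has no other Grade 3 or 4 event. The cohort's Grade 3 or 4 incidence then rises by 1/n. With the planned cohort sizes, and assuming all patients are in the safety population:

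- n = 13: 1/13 = 7.7 percentage points
- n = 19: 1/19 = 5.3 percentage points
- n = 70 (expanded cohort): 1/70 = 1.4 percentage points

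These are effects per case. The protocol gives no rate of life-threatening or fatal second primaries from which to project a number of cases.

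**The case against.** The strongest reply is that the information is not lost. Section 7.3.2 gives a worsening event a route to a higher grade. Section 7.2.2 requires the final outcome of every adverse event on the eCRF. Section 7.2.1.3 makes fatal and life-threatening separate grounds for seriousness. Section 8.3.3 has cause of death summarised and listed, and the SAE form carries no fixed grade. All of this stands, and it confines the problem to the graded summary and mainly to events already severe at first report.

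Four stronger readings may occur to a reader, and the documents do not support them.

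- **That the tables can never show a Grade 4 or 5 second malignancy.** Section 7.3.2 allows one for an event that worsens.
- **That the Grade 3 line mixes excised skin lesions with fatal cancers.** Section 7.3.4.2.2 asks for the type of malignancy and section 8.3.3 tabulates by preferred term, so different cancers fall on different lines. Mixing arises only in class or overall totals.
- **That minor lesions, such as a small basal cell carcinoma, are wrongly raised to Grade 3.** Without the CTCAE text, nothing shows that such a lesion grades lower. Table 7 does list some keratoacanthomas at Grade 2, but the Grade 3 sentence does not name keratoacanthoma. Its status as a second primary is only inferred from the way the section groups these events.
- **That the phase III melanoma trial measures the misgrading.** A footnote to Table 7 reports two of the 40 patients with cutaneous SCC graded 1 or 2 by investigators but reported as Grade 3. The same footnote describes Grade 3 as the grade according to CTCAE v4.0, so this is not evidence of a departure from it.

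**Conclusion.** The contradiction is real and lies wholly within the protocol. One sentence fixes Grade 3 without exception, while four other sections require CTCAE grading, independent assessment of severity, or tabulation on that basis. Under the literal rule, a second primary malignancy that is life-threatening or fatal at first report is recorded one or two grades too low, and a fatal one is placed in a primary safety variable where it does not belong.

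The weight is minor to moderate. Expedited reporting does not depend on grade, deaths remain visible through outcome and cause of death, and the primary efficacy analysis is untouched. In a cohort of 13 to 19 patients one misplaced death could still move the Grade 3 or 4 incidence by 5.3 to 7.7 percentage points, under the conditions stated above.

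The conclusion rests on two assumptions: that sites apply section 7.3.4.2.2 as written, and that Grades 4 and 5 in CTCAE carry the meaning given in Table 14.

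**What to change.** In the adverse event form instruction of section 7.3.4.2.2:

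1. Keep the request for the type of malignancy. Replace the fixed Grade 3 with: *graded according to NCI CTCAE v4.0, with Grade 4 or Grade 5 recorded where the event is life-threatening or fatal*.
2. State that the fixed Grade 3 for cutaneous SCC likewise does not override Grade 4 or 5. Otherwise the same defect remains for that event.
3. Add a cross-reference to sections 7.2.1.1, 7.3.1 and 7.3.2, so that initial grade, worst grade and the second-malignancy instruction are read together.

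Toxicity grade also enters Table 11 and the dose-limiting toxicity definition in section 6.3.2.2. The sponsor should check that those passages and the revised sentence are consistent; this point takes no position on their content.

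The cost is a few lines in the protocol and a matching change to the eCRF completion guidance. SAE reporting of every second primary stays mandatory whatever its grade. No new data are needed.
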